## 10. Protection of Human Subjects

This study will comply with all relevant ethical and regulatory requirements in each country, and will not be used for the conduct of marketing surveys or other marketing purposes. The study will comply with Amgen AE reporting standard operating procedures. This study and data collection will be conducted in accordance with the relevant local laws.

The Responsible Physician is also responsible for forwarding the following documents to Amgen or its representative for review before study initiation occurs:

- Signed and dated protocol signature page (Responsible Physician 's Agreement)
- Copy of the Central Ethics Board approval of the protocol, waiver for requirement of informed consent
- Patient/next-of-kin/body has provided informed consent (for countries where required per local laws and regulations)
- Up-to-date curriculum vitae of Responsible Physician and all co/sub-physicians
- Signed confidentiality agreement
- Signed study contract

The Responsible Physician will be charged with maintaining correct and comprehensive documentation, while the Amgen monitor/designee is tasked to ensure that the Responsible Physician is following the correct study protocol.

### 10.1 Informed Consent

For countries, where informed consent is required from patients, an initial sample informed consent form will be provided by Amgen for the Investigator to prepare the informed consent document to be used at his or her site. Updates to the template are to be communicated formally in writing from the Amgen Clinical Study Manager to the Investigator. The written informed consent document is to be prepared in the language of the potential subject population.

Where required by participating clinical sites for the collection of anonymized medical chart data, before a patient's participation in the study, the Investigator is responsible for obtaining written informed consent, where applicable by local regulations, from the subject or legally acceptable representative. The acquisition of informed consent is to be documented in the patient's medical records, and the informed consent form is to be signed and personally dated by the subject or legally acceptable representative and by the person who conducted the informed consent discussion. The original signed informed consent form is to be retained in accordance with institutional policy, and a

copy of the signed consent form is to be provided to the patient or legally acceptable representative. If a potential patient is illiterate or visually impaired and does not have a legally acceptable representative, the Investigator must provide an impartial witness to read the informed consent form to the patient and must allow for questions. Thereafter, both the patient and the witness must sign the informed consent form to attest that informed consent was freely given and understood.

Where required by local laws and regulations, consent will be sought from appropriate parties for the inclusion of deceased subject's data.

### **10.2 Institutional Review Board/Independent Ethics Committee**

A copy of the protocol, proposed informed consent form, other written subject/patient information, and any proposed advertising material must be submitted to the IRB/IEC or other relevant ethical review board for written approval. A copy of the written approval of the protocol and informed consent form must be received by Amgen before study can be executed.

The Investigator must submit and, where necessary, obtain approval from the IRB/IEC or other relevant ethical review board for all subsequent protocol amendments and changes to the informed consent document, as applicable. The Investigator is to notify the IRB/IEC or other relevant ethical review board of deviations from the protocol or SAE(s) occurring at the site and other AE reports received from Amgen, in accordance with local procedures.

The Investigator is responsible for obtaining annual IRB/IEC or other relevant ethical review board approval/renewal throughout the duration of the study. Copies of the Investigator's reports, where applicable by local regulations and the IRB/IEC or other relevant ethical review board continuance of approval must be sent to Amgen.

### **10.3 Patient Confidentiality**

The Investigator must ensure that the patient's confidentiality is maintained for documents submitted to Amgen.

- Medical records are to be identified by a unique patient identification number. The key to re-identify patients must not be shared with Amgen.
- Age is to be documented and formatted in accordance with local laws and regulations.
- Documents that are not for submission to Amgen (eg, signed informed consent forms, as applicable) are to be kept in confidence by the Investigator, except as described below.

In compliance with Local country regulations, it is required that the Investigator and institution permit authorized representatives of the company, of the regulatory agency(s), and the IRB/IEC or other relevant ethical review board direct access to review the patient 's original medical records for verification of study-related activities and data. Direct access includes examining, analysing, verifying, and reproducing any records and reports that are important to the evaluation of the study. The Investigator is obligated to inform and obtain the consent of the patient to permit such individuals to have access to his/her study-related records, including personal information.

Where required by local laws and regulations, consent will be sought from appropriate parties for the inclusion of deceased subject's data.

## **11. Reporting of Safety Information and Product Complaints**

### **11.1 Definition of Safety Events**

#### **11.1.1 Adverse Events**

An AE is any untoward medical occurrence in a subject/patient administered a pharmaceutical product(s) irrespective of a causal relationship with this treatment.

An AE can therefore be any unfavorable and unintended sign (including an abnormal laboratory finding, for example), symptom, or disease temporally associated with the use of a product(s), whether or not considered related to the product(s). The definition of an adverse event includes:

- Worsening of a pre-existing condition or underlying disease
- Events associated with the discontinuation of the use of a product(s), (eg, appearance of new symptoms)

It is the investigator's responsibility to evaluate whether an AE is related to an Amgen product prior to reporting the AE to Amgen.

#### **11.1.2 Serious Adverse Events**

A SAE is any AE as defined above that meets at least one of the following serious criteria:

- is fatal
- is life threatening (places the patient at immediate risk of death)
- requires in-patient hospitalization or prolongation of existing hospitalization
- results in persistent or significant disability/incapacity
- is a congenital anomaly/birth defect
- is an "other significant medical hazard" that does not meet any of the above criteria

A hospitalization meeting the regulatory definition for “serious” is any in-patient hospital admission that includes a minimum of an overnight stay in a healthcare facility.

“Other significant medical hazards” refer to important medical events that may not be immediately life-threatening or result in death or hospitalization, but may jeopardize the patient or may require intervention to prevent one of the other outcomes listed in the definition above. Examples of such events could include allergic bronchospasm, convulsions, and blood dyscrasias, drug-induced liver injury, events that necessitate an emergency room visit, outpatient surgery, or other events that require other urgent intervention.

### **11.1.3 Other Safety Findings**

Other Safety Findings (regardless of association with an AE) include:

- Medication errors, overdose/underdose, whether accidental or intentional, misuse, addiction or abuse, involving an Amgen product,
- Use of an Amgen product while pregnant and/or lactating,
- Transmission of infectious agents,
- Reports of uses outside the terms for authorized use of the product including off-label use,
- Accidental or occupational exposure,
- Any lack or loss of intended effect of the product(s).

### **11.1.4 Product Complaints**

Product Complaints include any written, electronic or oral communication that alleges deficiencies related to the identity, quality, durability, reliability, safety, effectiveness, or performance of a product, combination product, or device after it is released for distribution to market or clinic by either Amgen or by distributors and partners for whom Amgen manufactures the material. This includes any drug(s), device(s), or combination product(s) provisioned and/or repackaged /modified by Amgen. Drug(s) or device(s) or combination product(s) includes investigational product.

Product complaints of Blincyto will be collected and reported.

## **11.2 Safety Reporting Requirements**

This study is collecting information from patients prospectively.

### **11.2.1 Observation Period: Treatment Period (Blincyto Treatment – Treatment Start to 30 Days After Treatment Completion)**

The investigator is responsible for ensuring that safety events (SAEs, AEs, product complaints and other safety findings) observed by the investigator or reported by the

patient that occur after initiation of Blincyto in routine clinical practice through to 30 days after completion of treatment are recorded in the patient's appropriate study documentation. It is the investigator's responsibility to evaluate whether an adverse event is related to an Amgen product prior to reporting the adverse event to Amgen.

**11.2.1.1 Reporting Timelines: Treatment Period (Blincyto Treatment – Treatment Start to 30 Days After Treatment Completion)**

Safety events (SAEs, product complaints, and other safety findings) must be submitted as individual case safety reports to Amgen via the applicable Amgen Safety Reporting Form (paper or electronic) within 1 business day of data extraction from patient medical records. Non-serious AEs must be reported in an expeditious manner, not to exceed 15 calendar days of Investigator awareness.

**11.2.2 Observation Period: Post-treatment Period (From 31 Days After Blincyto Treatment Completion to End of Study)**

The investigator is responsible for ensuring that all SAEs, product complaints, and other safety findings observed by the investigator or reported by the patient that occur from 31 days after completion of treatment through to final chart abstraction, the start of another anti-cancer treatment, HSCT, or after 1 year, whichever is earliest, are also recorded in the patient's appropriate study documentation. Furthermore, all SAEs considered related to Blincyto (including probably/possibly/ doubtfully related) occurring after the start of another anti-cancer treatment, HSCT, or 1 year (whichever is earliest) through to the final chart abstraction should also be recorded in the patient's appropriate study documentation. It is the investigator's responsibility to evaluate whether an adverse event is related to an Amgen product prior to reporting the adverse event to Amgen.

All fatal SAEs must be reported throughout the study period from enrollment through to the end of study, regardless of relatedness.

The rationale for only requiring SAEs related to Blincyto (including probably/possibly/ doubtfully related) that occur from 31 days after completion of Blincyto treatment is that ALL patient populations present with multiple disease related events or may require further treatments which would not add to the safety profile of the product.

**11.2.2.1 Reporting Timelines: Post-treatment Period (From 31 Days After Blincyto Treatment Completion to End of Study)**

Safety events (SAEs, product complaints, and other safety findings) must be submitted as individual case safety reports to Amgen via the applicable Amgen Safety Reporting

Form (paper or electronic) within 1 business day of data extraction from patient medical records.

### 11.2.3 Protocol Exempt Safety Information

The adverse events to be collected in this study overall should include all specified adverse events indicated in the primary objective and all other adverse events except for those identified as very common in the pivotal clinical study, MT103-211, and described in the Blincyto SmPC, dated 26 Oct 2016. The rationale for exempting these very common events is that enough data already exists from clinical trials on very common events. As a result, the following table modified from the SmPC lists the adverse of events that are not required to be collected in this study:

| MedDRA System Organ Class                            | Very Common ( $\geq 1/10$ ) |
|--|-----------------------------|
| Metabolism and nutrition disorders                   | Hypokalaemia                |
|  | Hypomagnesaemia             |
|  | Hyperglycaemia              |
|  | Decreased appetite          |
| Psychiatric disorders                                | Insomnia                    |
| Respiratory, thoracic and mediastinal disorders      | Cough                       |
| Gastrointestinal disorders                           | Nausea                      |
|  | Constipation                |
|  | Diarrhoea                   |
|  | Abdominal pain              |
|  | Vomiting                    |
| Musculoskeletal and connective tissue disorders      | Back pain                   |
|  | Pain in extremity           |
|  | Arthralgia                  |
|  | Bone pain                   |
| General disorders and administration site conditions | Fatigue                     |
|  | Chest pain                  |

If any of the exempted events have a fatal outcome, they should be considered as a serious adverse event and must be reported individually within 1 business day of data extraction from patient medical records.

All safety information that is not specified in this section including all fatal events are to be collected and submitted to Amgen within the specified time frame.

If the EDC system is unavailable to the site staff to report the AE, the information is to be reported to Amgen via a paper Adverse Event Contingency Report Form within

1 business day of data extraction from patient medical records. For EDC studies where the first notification of an Adverse Event is reported to Amgen via the Adverse Event Contingency Report Form, the data must be entered into the EDC system when the system is again available.

See [Appendix C](#) for sample Safety Report Form(s), [Appendix D](#) for Additional Safety Reporting Information regarding the AE grading scale used in this study, and [Appendix E](#) for sample Pregnancy and Lactation Notification Forms.

The Investigator may be asked to provide additional information for any event submitted, which may include a discharge summary or extracts from the medical record. Information provided about the event must be consistent with information recorded on study Case Report Forms (CRFs) where safety data may also be recorded (eg, Event CRF).

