## **8. Research Question and Objectives**

### **8.1 Primary**

The first primary objective is to characterise the safety profile of Blincyto in routine clinical practice in countries in Europe by characterising specific AEs. These events include:

- Neurologic adverse events
- Opportunistic infections
- **Cytokine release syndrome**

The second primary objective is to estimate the frequency and type of medication errors identified in patient charts.

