## **9.7.2.3 Analysis of the Primary, Secondary and Exploratory Endpoint(s)**

### **9.7.2.3.1 Primary Endpoint(s)**

*Specified adverse events:*

Subject incidence proportions (and 95% CIs) for each of the specified adverse events will be summarised. For each of the specified events, incidence will be tabulated by system organ class and preferred term, and preferred term only. Incidence tables will also be presented with respect to time on Blincyto at the patient level (incidence rate) and event level (event rate). KM estimates for time to first onset of each specified event will be provided. A summary of days experiencing specified events and days experiencing resolved/recovered specified events will also be presented. Tables will be presented overall, and by seriousness (serious, fatal) and severity (grade  $\geq 3$ , grade  $\geq 4$ , events leading to discontinuation of Blincyto, events leading to interruption of Blincyto) of event. Tables relating to specified AEs will also be summarised by the patient subgroups listed in Section 9.7.2.3.4. Tables will additionally be presented for specified AEs that are considered related to Blincyto treatment.

*Blincyto medication errors:*

When possible, medication errors may be classified as error with ADR, error without harm, intercepted error and potential error. The number and proportion of medication errors will be summarised overall, by medication error classification, by place of occurrence, and by whether the error resulted in an underdose or overdose of Blincyto. AEs related to medication errors will also be summarised.

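### The exempt-event list makes no exception for events attributed to a medication error, so the planned summary of harm from errors may understate that harm

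*Protocol*

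**What the plan says.** Protocol 8.1 sets the aim: "The second primary objective is to estimate the frequency and type of medication errors identified in patient charts". Section 9.3.2.1 defines the endpoint as the proportion of Blincyto administrations with an error, together with a description of error types. Its definition of an error covers failures that cause harm and failures that only could.

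Section 9.7.2.3.1 adds two outputs on harm. The first is conditional, to be produced where feasible: "medication errors may be classified as error with ADR, error without harm, intercepted error and potential error". The second carries no condition: "AEs related to medication errors will also be summarised".

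Section 11.2.3 sets the scope of collection. The events collected "should include all specified adverse events indicated in the primary objective and all other adverse events except for those identified as very common"; that label is taken from the pivotal trial. The table of 17 terms that follows "lists the adverse of events that are not required to be collected in this study". The reason given is: "The rationale for exempting these very common events is that enough data already exists from clinical trials on very common events". The one exception is: "If any of the exempted events have a fatal outcome, they should be considered as a serious adverse event".

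Section 11.1.3 handles the error separately. Its list opens with the words "Other Safety Findings (regardless of association with an AE) include", and errors, overdosing and underdosing with the product are among the entries.

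**The concern.** The error and the harm it causes are collected under different rules. A recorded error always stays in the data. A non-fatal exempt event that the error caused need not be recorded, even when the chart shows it and the treating physician attributes it to the error. Since events can be lost only on the harm side, any resulting bias makes errors look more benign.

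The stated reason for the exemption does not reach these events. Trial data on very common terms describe how often they occur in treated patients generally. They do not describe what follows an incorrectly prepared or administered dose, which is part of what this study was set up to report.

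At stake are two descriptive outputs reported under a primary endpoint of an imposed safety study: the table of events related to errors, and the harm split if it is built from collected events.

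**Working it through.** The protocol states no figure on this point, so there is nothing to reproduce. The check sets the sections side by side and then illustrates the size.

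**1. Is there an exception for error-related events?** Section 11.2.3 exempts 17 terms: 4 metabolic, 1 psychiatric, 1 respiratory, 5 gastrointestinal, 4 musculoskeletal and 2 general (4 + 1 + 1 + 5 + 4 + 2 = 17). It makes an exception for fatal outcome and for nothing else.

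**2. Does another section close the gap?**
- The sample contingency form in Appendix C asks for all adverse events unless the protocol instructs otherwise, so it defers to the exemption.
- Appendix B lists other safety findings and adverse events as separate items, and shows no item for harm resulting from an error. The full eCRF is not shown, so such a field may exist, but the protocol does not state one.
- Section 9.9 admits that errors may go unrecorded. It does not mention recorded errors whose harm is an exempt event.
- Section 11.2.1 asks for serious events without qualification, while 11.2.3 restores exempt events only when fatal. Whether a serious but non-fatal exempt event is collected is therefore unclear.

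**3. What remains collected?** Fatal events, the specified events (neurologic events, opportunistic infections, cytokine release syndrome) and every term not on the list. An error with any such event still shows harm.

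**4. Are the exempt terms marginal?** Section 7.1 names eight events reported in at least 20% of trial patients. Four are exempt (fatigue, nausea, hypokalaemia, diarrhoea) and four are not (pyrexia, headache, peripheral oedema, tremor). This shows that the list covers frequent terms. It does not show how often an exempt term is the only harm from an error.

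**5. Illustration of size (all inputs assumed).** Let h be the true share of recorded errors that caused harm. Let q be the share of those harmful errors whose only harm is a non-fatal exempt event that goes uncollected. If the harm class is built from collected events, the reported share is h × (1 − q).

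| True share h | q = 0 | q = 10% | q = 25% | q = 50% |
|---|---|---|---|---|
| 10% | 10% | 9% | 7.5% | 5% |
| 30% | 30% | 27% | 22.5% | 15% |
| 50% | 50% | 45% | 37.5% | 25% |

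The middle row is, for example, 0.30 × (1 − 0.25) = 0.225. The number of errors enters none of these reductions, so the proportion of administrations with an error is the same for every q.

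**The case against.** A reader might infer that errors followed only by exempt events will be placed in the class without harm, and that the second primary endpoint is thereby biased. The documents do not support either step. The classification is optional, and its data source is not stated; that may be settled in the eCRF or the analysis plan. The endpoint in 9.3.2.1 counts errors with or without resulting harm, so no exempt term can change it.

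A second argument is that harm can reach the sponsor by another route. Errors are submitted as individual case safety reports. The sample form in Appendix C has outcome and narrative fields, and the investigator may be asked for chart extracts. The list also says only that the terms are not required, so a site may record them anyway. This stands in part: harm may be known in some cases. But a free-text route and voluntary recording would vary by site, and neither gives a consistent basis for a table of related events.

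A third argument concerns the remedy. Very common events have a high background rate, and the definition in 11.1.1 makes an event adverse irrespective of cause. Collecting every exempt event near an error would bring in background nausea or fatigue and could count it as an adverse drug reaction. This stands, and the exception should be limited to events attributed to the error.

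A fourth is timing. Data collection was planned to start in Q1 2017 with new patients for 5 years, that is to about Q1 2022, and this version is dated 9 September 2022. Unless enrolment was extended, as 9.5 allows, most treatment periods are already past. This also stands, and it adds to the cost of the fix.

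**Conclusion.** The point holds in a limited form. Section 11.2.3 makes no exception, other than for fatal outcome, for exempt events attributed to a medication error. The summary of events related to errors planned without condition in 9.7.2.3.1 can therefore miss them, and so can a harm split that relies on collected events. The effect runs one way, towards less apparent harm, and 9.9 does not disclose it.

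The size is unknown. The percentages in the illustration rest on assumed values of h and q, on exempt events going uncollected, and on the harm class being built from collected events. If sites record these events anyway, or if harm is marked on the error report independently of the list, the understatement of the harm split shrinks or disappears. The outputs affected are descriptive, and the gap is cheap to close.

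**What to change.** In 11.2.3, add that the exemption does not apply to an event the investigator considers related to a Blincyto medication error, overdose or underdose, and that such events are collected and linked to the error. In 9.7.2.3.1, state that the harm class and the table of related events are based on these linked, attributed events. Flag the added records so that they do not enter the general incidence tables, where the same terms would otherwise be ascertained only in patients with an error.

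The cost is a few extra adverse event records, an instruction to abstractors, and a limited re-check of charts already abstracted for patients with a recorded error. Where that re-check is not possible, 9.9 should say that the exempt terms are missing from the summary of harm from errors.

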## **7.2 Rationale**

As a new treatment for adults with R/R Philadelphia chromosome-negative (Ph-) B-precursor ALL, it is important to understand the safety and efficacy of Blincyto as it is administered in routine clinical practice. The clinical development program for the treatment of R/R Ph- B-precursor ALL initially consisted of three single-arm studies: a phase 1/2 study of Body Surface Area (BSA)-based dosing in children (MT103-205, completed, N = 70), a dose-ranging study of BSA-based dosing in adults (MT103-206, completed, N = 36), and the pivotal trial (MT103-211, completed, N = 189), a phase 2 study of a flat dose regimen in adults. To date, the clinical trial experience with Blincyto has been limited to these three studies; however, the recently completed phase 3 randomized confirmatory study of adults with R/R ALL (MT103-311 [TOWER]) will provide additional comparative efficacy and safety data in 2016. Despite the forthcoming increased amount of safety data, the overall experience is limited to the clinical trial populations with limited patient exposure, treatment duration and follow-up and in which exclusion criteria were applied. Therefore, more data on existing safety concerns in routine clinical practice and any data on exposure in so far unstudied populations are considered essential to further understand the benefit-risk of Blincyto.

Following recommendations from the Committee for Medicinal Products for Human Use (CHMP) and Pharmacovigilance Risk Assessment Committee (PRAC) review of the marketing authorisation application for Blincyto, this post-authorisation safety study (PASS) was developed to assess real-life safety and efficacy of Blincyto. This imposed observational PASS study will be conducted in selected countries in Europe. Blincyto safety and efficacy among patient subgroups defined by demographic and clinical factors (eg, late first-relapse [LFR], those with existing hepatic impairment) will complement the evidence from the Clinical Development program. It is also important to determine the frequency and type of medication errors that occur in routine clinical practice.

Dose adjustments after an occurrence of a severe or life-threatening adverse event (AE) are recommended in the Summary of Product Characteristics (SmPC). This study will also describe the treatment practices employed by physicians after severe or life-threatening AEs using the medical record review.

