### **9.7.2.3.2 Secondary Endpoint(s)**

*All adverse events:*

Subject incidence proportions (and 95% CIs) for all AEs collected in this study (see Sections 11.2.1 to 11.2.3) will be summarised and tabulated by system organ class and preferred term, and preferred term only. Incidence tables will also be presented with respect to time on Blincyto at the patient level (incidence rate) and event level (event rate). Tables will be presented overall, and by seriousness (serious, fatal) and severity (grade  $\geq$  3, grade  $\geq$  4, events leading to discontinuation of Blincyto, events leading to interruption of Blincyto) of event. Tables relating to AEs will also be summarised by the patient subgroups listed in Section 9.7.2.3.4. Tables will additionally be presented for AEs that are considered related to Blincyto treatment.

*Efficacy:*

Summaries of endpoints outlined in Section 9.3.2.2 in relation to efficacy overall and KM summaries as described in Section 9.7.2 will be performed. The assessment of MRD may also be performed by method of MRD assessment (PCR or flow cytometry). The 1-year and 100-day mortality after allogeneic HSCT will be summarised with the 1-year and 100-day KM rate and the additional KM summaries described in Section 9.7.2. For this endpoint, OS will be measured starting from the date of allogeneic HSCT in the subset of patients who undergo an allogeneic HSCT and OS endpoint summaries will be provided as described in Section 9.7.2.

*Blincyto utilisation & select health care resource use:*

Summaries of endpoints outlined in Section 9.3.2.2 in relation to Blincyto utilisation & select health care resource use will be summarised.

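### Non-fatal serious cases of 17 exempt adverse-event terms fall under conflicting collection rules, so SAE incidence can only equal or understate the truth

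*Protocol*

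**What the plan says.** Section 11.2.3 defines what is collected: it "should include all specified adverse events indicated in the primary objective and all other adverse events except for those identified as very common", judged by the pivotal study and the product information. A table of 17 terms follows, which "lists the adverse of events that are not required to be collected in this study". The exemption goes by term alone. It has one override, for fatal cases: "If any of the exempted events have a fatal outcome, they should be considered as a serious adverse event and must be reported individually". The closing rule, "All safety information that is not specified in this section including all fatal events are to be collected and submitted to Amgen", restores nothing further for a listed term.

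Section 11.2.1 makes the investigator responsible for recording "safety events (SAEs, AEs, product complaints and other safety findings) observed by the investigator" up to 30 days after treatment. Section 11.2.2 asks for all SAEs from day 31 until the earliest of several cut-offs, and Appendix B footnote l repeats this. None of the three refers to the exemption.

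On the analysis side, section 9.7.2.3.2 summarises the AEs collected under sections 11.2.1 to 11.2.3: "Tables will be presented overall, and by seriousness (serious, fatal) and severity", the last including grade 3 or higher, grade 4 or higher, and events leading to discontinuation or interruption. Section 9.7.2.3.3 tabulates the incidence of post-treatment SAEs, and of SAEs by time interval including the treatment period, without restricting them to collected events.

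**The concern.** Under section 11.1.2 an in-patient hospitalisation is enough to make an event serious. A non-fatal admission for vomiting, diarrhoea or chest pain is therefore an SAE that section 11.2.2 and footnote l require and section 11.2.3 does not. Because the exempt terms are merely not required, a site may also record some of them voluntarily. Capture may then differ between sites.

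Two outputs suffer. An SAE incidence from section 9.7.2.3.3 would be read as covering all SAEs when it may not. The breakdowns by grade, interruption and discontinuation would omit severe or treatment-changing cases of the exempt terms. The section 9.3.2.2 endpoint on treatment changes after AEs, stratified by event type, also loses the triggering event when that event is exempt.

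Section 9.9 intends to use trial data as context but does not list the exemption as a limitation. The stated rationale, that enough data exist, concerns how often these terms occur. It says little about serious or treatment-stopping cases in routine practice, where section 7.2 holds that "any data on exposure in so far unstudied populations are considered essential".

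**Working it through.** **Rules side by side, for a non-fatal SAE whose term is one of the 17**

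| Place in protocol | Collected? |
|---|---|
| 11.2.1 (treatment period) | Yes; SAEs and AEs, no exception named |
| 11.2.2 (day 31 to the earliest cut-off) | Yes; all SAEs |
| Appendix B footnote l | Yes; all SAEs in the same window |
| 11.2.3 | Not required; only a fatal outcome restores it |
| 9.7.2.3.2 (analysis) | Counted if collected |
| 9.7.2.3.3 (analysis) | Counted as an SAE, no qualifier |

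The label in 9.7.2.3.2 points to sections 11.2.1 to 11.2.3 together, so it carries the disagreement with it and does not settle it.

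**Count.** The table lists 4 metabolic, 1 psychiatric, 1 respiratory, 5 gastrointestinal, 4 musculoskeletal and 2 general terms: 4 + 1 + 1 + 5 + 4 + 2 = 17. Of the eight most common TEAEs named in section 7.1, four are exempt: fatigue, nausea, hypokalaemia and diarrhoea. Of the six most frequent TEAEs of grade 3 or higher named there (febrile neutropenia, neutropenia, leukopenia, anaemia, thrombocytopenia, pneumonia), none is exempt.

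**Direction.** Leaving out events can only remove patients from a numerator. Each affected incidence is therefore equal to or below the incidence with full collection.

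**Size.** The protocol gives no rate of serious, grade 3 or higher, or treatment-stopping cases for these terms, so there is no figure of its own to reproduce and no shortfall can be derived. The following is an illustration only. It assumes:

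- each term occurs in 10% of patients, the lower bound of the class in the 11.2.3 table, carried over to this cohort (0.10 × 200 = 20 patients per term at the target of about 200 in section 9.5);
- a share s of these cases is serious and non-fatal (assumed, 1% to 10%);
- terms are independent, and no such case is collected;
- the collected SAE incidence is b (assumed, 30% to 60%), independent of the missing events.

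Proportion of patients with at least one missing SAE: m = 1 − (1 − 0.10 s)^17. Shortfall in SAE incidence: (1 − b) × m.

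| s | m | Patients of 200 | Shortfall, b = 30% | b = 50% | b = 60% |
|---|---|---|---|---|---|
| 1% | 1.7% | 3.4 | 1.2 points | 0.8 | 0.7 |
| 5% | 8.2% | 16.3 | 5.7 | 4.1 | 3.3 |
| 10% | 15.7% | 31.4 | 11.0 | 7.9 | 6.3 |

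Overlap between missing and collected SAEs, or partial capture, makes the shortfall smaller. The frequency class says nothing about the window from day 31, so the illustration speaks to the treatment period only.

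**The case against.** The strongest reply is that section 11.2.3, by its heading and scope, is the exception to the general rules before it. Section 11.2.1 also asks for AEs without exception, yet nobody would take non-serious nausea to be required. The fatal-only override makes sense only if non-fatal serious cases are exempt. This is a fair reading and perhaps the intended one. But no section says so, and the wording on all SAEs in 11.2.2 and footnote l points the other way. If it is the intended reading, the unqualified SAE tables in 9.7.2.3.3 still need a label.

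Several stronger inferences are tempting and are not supported:

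- *The primary safety result is compromised.* It is not; section 11.2.3 keeps all specified AEs in collection.
- *The tables in 9.7.2.3.2 are presented as complete.* They are not; objectives, endpoints and analysis all speak of AEs collected in this study.
- *The grade 3 or higher profile is lost.* The six most frequent such events in section 7.1 all stay in collection.
- *There are no trial data on children.* Section 7.2 lists a completed paediatric study of 70 patients. What stands is that the exempt list derives from a pivotal study in adults.
- *Missing SAEs can be counted.* Multiplying 17 terms by 10% of 200 gives 340 patient-term occurrences, not patients, and rests on a rate from another population. Any serious share applied to it is unsourced.
- *Sites do report differently.* Section 9.6 provides training on the eCRF and section 9.8 data review and source verification. Divergence is possible, not shown.

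Some information also survives elsewhere. Treatment-period hospitalisations and drug administration are collected under Appendix B regardless of the exemption; what is lost is attribution to the exempt event. After treatment, footnotes e and f collect concomitant medication and hospitalisation only in the case of SAEs, so that backstop is missing.

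**Conclusion.** The point stands as a conflict between collection rules, with a known direction of bias in secondary and other safety outputs. Non-fatal serious cases of 17 terms are required by 11.2.2 and footnote l and not required by 11.2.3, and 9.7.2.3.3 reports SAE incidence as if the question did not arise. The affected incidences equal or understate the truth. This matters most for SAEs and less for the grade, interruption and discontinuation tables, which carry a partial label.

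The direction needs no assumption beyond some non-fatal serious, severe or treatment-changing cases going unrecorded. The size cannot be determined from the documents. The range of 0.7 to 11.0 percentage points depends wholly on the assumed inputs and should not be quoted as an estimate. The matter should be corrected because it changes what the SAE tables can be taken to show.

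**What to change.** 1. Reconcile 11.2.3 with 11.2.1, 11.2.2 and Appendix B footnote l by stating whether the exemption covers non-fatal SAEs, and add the cross-references. Preferably, for charts still being abstracted, limit the exemption to non-serious events that caused no treatment change.
2. Where charts are closed, exclude the 17 terms, other than fatal cases, uniformly from the SAE, grade 3 or higher, and interruption and discontinuation totals in 9.7.2.3.2 and 9.7.2.3.3, and say so in the table titles. If open and closed charts are pooled, use this exclusion for the pooled totals so that two collection rules are not mixed.
3. List the exclusion in 9.9 as a downward bias, including for any comparison with trial data.

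Timing limits the first step. Data collection was planned from Q1 2017 with five years of new patients, so inclusion was due to end about Q1 2022, before this amendment of September 2022 (section 9.5 allows an extension for late first-relapse patients). Most treatment periods are probably over, and re-abstracting completed charts would be costly. The cost is a little extra abstraction for open charts, or slightly lower and explicitly labelled totals; steps 2 and 3 need no new data.
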